## 1. Objectives

The purpose of this statistical analysis plan is to provide details of the analyses described in “14. Statistical Analysis” of the protocol (Version: 1.0).

## 2. Analysis Sets

When the full analysis set (FAS) is used for analysis, the analysis will be performed based on the treatment groups to which the subjects have been assigned. When the safety set (SS) or pharmacokinetic analysis set (PKS) is used for analysis, the analysis will be performed based on the actual treatment received by the subjects.

- 1) FAS  
Subject population which excludes subjects who deviated GCP, who did not receive any study drug, who discontinued prior to Period I, who was ineligible to the major inclusion/exclusion criteria, and who could not obtain any of the primary endpoint data.
- 2) SS  
Subject population which excludes subjects who deviated GCP, who did not receive any study drug, and who discontinued prior to Period I.
- 3) PKS  
Set of subjects excluding subjects who have no plasma drug concentration data at all from subjects in the SS

The correspondence between analysis variables and analysis sets is shown in [Table 2-1](#).

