However, the study drug may be continued in both subjects who complete Period I and early transition subjects if the investigator judges that tangible clinical benefit from the use of study drug is evident, with reference to the following a) to c).

- a) If the platelet count is obviously increased (eg, if the platelet count increases $20000/\mu L$ or more from Day 1 and the platelet count is $30000/\mu L$ or more)
- b) Reduction in bleeding events
- c) Reduction in rescue therapy
- 3) Subjects' voluntary request to discontinue the study (discontinuation due to adverse events is classified as 1) and discontinuation due to lack of efficacy is classified as 2)).
- 4) Significant protocol deviations during the study period
 - If GCP violations are found
 - If it is found that the subject of the protocol, inclusion criteria, or exclusion criteria are not met after case registration
 - If the investigator judges that the subject does not comply with the protocol and causes health damage to the subject due to continuation of the study
- 5) Pregnancy
- 6) Termination of the entire study
- 7) Discontinuation of the study at the study institution in question
- 8) Unobservable or loss to follow-up
 - If the subject cannot be contacted and the continuation of the study becomes impossible
- 9) In addition, if the investigator judges that discontinuation of the study is necessary (the reason is recorded in the Case Report Form [CRF] in detail)

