13.3 Procedure for Discontinuation/suspension

The following procedure should be taken to discontinue or suspend the study.

- 1) When the sponsor discontinues or suspends part of the study or the entire study, the sponsor will promptly notify the head of each study institution of the fact and detailed reason in writing.
- 2) When the principal investigator discontinues or suspends the study, the principal investigator will promptly report the fact and reason to the head of the study institution in writing.
- 3) When the head of each study institution receives the notification of the discontinuation/suspension of part of the study or the entire study from the sponsor, the

head of each study institution will immediately notify the principal investigator and IRB of the fact in writing and then report the reason for discontinuation/suspension in writing. When the head of the study institution receives the notification from the principal investigator, the head of the study institution will immediately notify the sponsor and IRB of the fact in writing and then report the reason for discontinuation/suspension in writing.

When the principal investigator receives the notification of the discontinuation/suspension of the study, the principal investigator will promptly inform the subjects with the study drug administration of the fact and take appropriate follow-up measures.

14. Statistical Analysis

Data analysis will be performed by the associate statistician as directed by the statistical analysis manager. The main analysis methods are as specified below. The detailed analyses methods will be specified in the statistical analysis plan to be prepared separately before the data from Period I are locked. Any necessary analysis other than the pre-specified analyses will be performed using an appropriate method at the discretion of the statistical analysis manager. SAS 9.4 or later will be used as the analysis software.

Inclusion/exclusion of subjects in analysis sets and handling of data will be determined before data lock in Period I.

Statistical tests will be performed using a two-sided significance level of 5%. Summary statistics will include the number of subjects, mean, standard deviation, minimum, median, maximum, and quartile. Unless otherwise specified, data will be tabulated for each analysis group, each period, and each time point.

The time points of analysis are shown in this chapter. The time window of each time point will be specified separately.

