14.1 Analysis Sets

Analysis will be performed based on the assigned treatment when the full analysis set (FAS) is used as the analysis set. Analysis will be performed based on the actual treatment when the safety set (SS) and pharmacokinetic analysis set (PKS) are used as an analysis set.

- FAS: Subject population which excludes subjects who deviated GCP, who did not receive any study drug, who discontinued prior to Period I, who was ineligible to the major inclusion/exclusion criteria, and who could not obtain any of the primary endpoint data.
- SS: Subject population which excludes subjects who deviated GCP, who did not receive any study drug, and who discontinued prior to Period I.
- PKS: Set of subjects excluding subjects who have no plasma drug concentration data at all from subjects in the SS

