14.6 Safety

SS will be used as the safety analysis set. Safety will be analyzed by the analysis groups and Day 1 of each period will be considered as the baseline. Day 1 of Period I will be considered as the baseline for the evaluation of the long-term administration of R788. In addition, the analysis for the Non-dosing period and Period III will be performed only for "14.6.1 Adverse events and adverse drug reactions" and "14.6.2 ITP Bleeding Score", and the analysis for R788 treatment period will be performed only for "14.6.1 Adverse events and adverse drug reactions."

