### **6.5.3 Multiplicity for multiple analysis sets**

Not applicable because only the FAS, SS, and PKS will be used for the analysis of efficacy, safety, and pharmacokinetics, respectively.

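### The safety set excludes dosed subjects who deviated from GCP, with no defined threshold; if there is one, that subject's events and exposure leave every planned safety table

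*SAP*

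**What the plan says.** SAP 2 defines SS in one sentence: "Subject population which excludes subjects who deviated GCP, who did not receive any study drug, and who discontinued prior to Period I". Protocol 14.1 carries the same three exclusions ("SS: Subject population which excludes subjects who deviated GCP, who did not receive any study drug, and who discontinued prior to Period I"), so the two documents agree. For SS, "the analysis will be performed based on the actual treatment received by the subjects".

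No other set is used for safety. Protocol 14.6 states "SS will be used as the safety analysis set". SAP Table 2-1 assigns all safety variables to SS, together with demographics and treatment compliance. SAP 6.5.3 confirms that there is no alternative: "Not applicable because only the FAS, SS, and PKS will be used for the analysis of efficacy, safety, and pharmacokinetics, respectively". The pharmacokinetic set is drawn from SS.

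Protocol 5.3.1, item 4), lists GCP violations among the reasons to withdraw a subject during the study ("If GCP violations are found"). The opening of Protocol 14 fixes the timing: "Inclusion/exclusion of subjects in analysis sets and handling of data will be determined before data lock in Period I".

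SAP 8.1 reports, for all randomized subjects, how many are in or out of each set. SAP 8.2 tabulates reasons for discontinuation, including one for significant deviation.

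**The concern.** A safety set should follow exposure. What the drug does to a person who has taken it does not depend on whether the trial's conduct met GCP for that person, so removing a dosed subject can only lose exposure and events.

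The plan otherwise accepts this principle. The efficacy set also drops subjects who fail major eligibility criteria and those without primary endpoint data. SS keeps both kinds and groups them by treatment received. The GCP clause is the one exception, and neither document gives a reason for it.

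Nor does either document say what counts as a GCP deviation for this purpose: how serious it must be, or whether it must make the data unusable, as missing consent would. Protocol 13.2 recognises GCP violations by the sponsor, an institution or a principal investigator, and the SS definition does not say whether such a violation would remove the subjects concerned. With 16 and 8 subjects planned, a single exclusion would be visible in the safety results.

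**Working it through.** The plan states no figure on this point. Its only design figure is the 89% in Protocol 8.9.2 (chance that the R788 response rate exceeds placebo at 16 versus 8, with 17.8% and 2.0%). An exact binomial sum with ties not counted gives 0.893, which agrees. It concerns the primary endpoint and is unaffected here.

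**Step 1: which clause can remove a dosed subject?**
- No study drug received: undosed by definition.
- Discontinued before Period I: also undosed, because Protocol 8.2 starts Period I after the Day 1 administration.
- Deviated GCP: the only clause with any effect on a dosed subject. Requiring all three conditions together would make the definition pointless, so they are read as alternatives.

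Protocol 5.3.1 4) shows that GCP violations in subjects already under treatment are foreseen.

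**Step 2: where would that subject's data still appear?**
- Adverse event tables (SAP 12.1), bleeding score, laboratory tests and vital signs: SS under Table 2-1, so not there.
- Listings of deaths, serious events and events of interest (SAP 12.6): in the safety section with no other set named, so SS, and not there.
- Exposure and compliance (SAP 10): SS, so not there.
- SAP 8.1: counted as excluded.
- SAP 8.2: counted, if withdrawn, under the reason for withdrawal.

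**Step 3: size at the planned numbers** (16 R788 and 8 placebo, Protocol 8.9.1; all assumed dosed).

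Share of an arm lost per excluded subject: 1/16 = 6.25% on R788; 1/8 = 12.5% on placebo.

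Exact (Clopper-Pearson) 95% limits:
- for 1 event in n, lower = 1 − 0.975^(1/n), and the upper limit U solves (1 − U)^n + nU(1 − U)^(n−1) = 0.025;
- for 0 events in n, upper = 1 − 0.025^(1/n).

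Sole event in the excluded subject:
- R788: 1/16 = 6.3% (0.2% to 30.2%) becomes 0/15 = 0% (upper limit 1 − 0.025^(1/15) = 21.8%).
- Placebo: 1/8 = 12.5% (0.3% to 52.7%) becomes 0/7 = 0% (upper limit 1 − 0.025^(1/7) = 41.0%).

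One of two events in the excluded subject:
- R788: 2/16 = 12.5% (1.6% to 38.3%) becomes 1/15 = 6.7% (0.2% to 31.9%).

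These counts are plausible for this drug. Protocol 1.4.1 gives neutropenia in 6% on R788 overseas, so 16 × 0.06 = 0.96 expected cases. It gives serious adverse events in 13/102, so 16 × 13/102 = 2.0.

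**The case against.** Several stronger readings are tempting, and the documents do not support them.

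- **That excluded subjects vanish without trace.** They do not. SAP 8.1 and Protocol 14.3 count exclusions from each set, and SAP 8.2 counts withdrawals for significant deviation or adverse events. What is missing is narrower: the reason for exclusion, the exposure and the events.
- **That the exclusion is open-ended.** In time it is bounded, because set membership is settled before the Period I data lock and the assignment table is opened only after Period I data are fixed (Protocol 8.8.6). In kind it is also narrower than protocol deviations at large. Protocol 5.3.1 4) separates GCP violations from ineligibility found after registration and from non-compliance, and SS names only the first. The threshold is undefined, not unlimited.
- **That a GCP finding in the open-label periods must conflict with the membership rule or be judged with treatment known.** Applied as written, the rule closes membership, and a later finding removes no one. The conflict arises only if the rule is broken.
- **That events have been lost.** No document reports a dosed subject with a GCP deviation. If there is none, the present and proposed sets are identical.

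It is also fair to say that adverse events still reach the case report form (Protocol 10.15.1) and that serious ones are notified within 24 hours (Protocol 12.2.2), whatever the analysis set. The illustrated intervals overlap widely. Finally, SAP 3.0 was revised for the second data cutoff, so Period I membership has probably been decided and a new definition could be a change made after unblinding.

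All of this limits the point. None of it puts an excluded subject's exposure or events back into the safety tables or listings.

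**Conclusion.** The point stands as a conditional one. Under the stated rule, a dosed subject judged to have deviated from GCP is outside the only set used for safety, and that subject's exposure and adverse events would be absent from every planned safety table and listing. Each such subject would remove 6.25% of the planned R788 arm or 12.5% of placebo. The change from 1/16 to 0/15 is a worst case: it assumes planned enrolment, everyone dosed, and one excluded R788 subject who had the only event of its kind. The likelihood of such a subject cannot be judged from the documents. The definition is still worth changing, because the rule can only lose safety information and the change costs little.

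**What to change.** In SAP 2 and Protocol 14.1, define SS as all subjects who received at least one dose of study drug, analysed by treatment received. Leave out a dosed subject only where the data may not lawfully be used, for example where there is no valid consent. List each such subject with the reason and, as far as permitted, exposure and adverse events.

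Record the change in SAP 16. If it is made after Period I unblinding, state there whether any subject's membership changes; if none does, the results are unaffected.

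The cost is one definition in each document and at most a short listing. The pharmacokinetic set follows automatically because it is drawn from SS. The small downside is that data from a subject with a GCP deviation enter the safety tables.

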**Table 2-1 Analysis Variables and Analysis Sets**

Variables evaluated	Variables analyzed	Analysis set
Demographics and other baseline characteristics	Subject demographics	SS
	Other	SS
Treatment compliance	All variables	SS
Efficacy	All variables	FAS
Safety	All variables	SS
Pharmacokinetics	All variables	PKS

## 3. Analysis Group

Unless otherwise specified, the analysis will be performed on the following subjects and data. For FAS analysis, “treated subjects” will be handled as “randomized subjects.”

- 1) Evaluation in Period I
  - R788 group: Period I data of subjects who received R788 in Period I
  - Placebo group: Period I data of subjects who received placebo in Period I
- 2) Evaluation during long-term treatment of R788
  - R788 group: The analysis will be performed on the following subjects and data:
    - Period I data of subjects who received R788 in Period I
    - Period II data of subjects who received R788 in Period I, completed treatment with R788 in Period I and transitioned to Period II (subjects on long-term treatment of R788)

3) Evaluation in Period II

- R788-R788 group: Period II data of subjects who received R788 in Period I and early transitioned to Period II after discontinuing Period I
- P-R788 group: Period II data of subjects who received placebo in Period I and transitioned to Period II

4) Evaluation in non-dosing period

- R788 group: Non-dosing period data of subjects who transitioned to the non-dosing period (subjects who transitioned from Period II to Period III without non-dosing period are excluded).

5) Evaluation in Period III

- R788 group: Period III data of subjects who transitioned to Period III

6) Evaluation in R788 treatment period

- R788 group: The analysis will be performed on the following subjects and data:
  - Data from Period I, Period II, and Period III of subjects who received R788 in Period I
  - Data from Period II and Period III of subjects who received placebo in Period I and transitioned to Period II

7) Evaluation in the entire study period

- R788-R788 group: Data from Period I, Period II, non-dosing period, and Period III of subjects who received R788 in Period I
- P-R788 group: Data from Period I, Period II, non-dosing period, and Period III of subjects who received placebo in Period I

**CONFIDENTIAL**

Kissei Pharmaceutical Co., Ltd.

Protocol No.: R788-1301

Statistical Analysis Plan

Version: 3.0

[figure not shown]
[figure not shown]
[figure not shown]

Figure 3-1

Analyzed subjects and data for each evaluation

## 4. General Principles of Statistical Analysis

- Statistical tests will be performed using a two-sided significance level of 5%.
- Summary statistics will include the number of subjects, mean, standard deviation, minimum, median, maximum, and quartiles.
- Unless otherwise specified, data will be summarized for each analysis group, each period, and each analysis visit.
- For confidence intervals (CIs) of proportions, Clopper-Pearson exact two-sided 95% CIs will be presented for each group, and Chan-Zhang exact two-sided 95% CIs will be presented for between-group differences.

## 5. Data Handling

### 5.1 Number of Digits to be Reported for Calculated Values

- 1) P values and statistics  
Values will be rounded down to the third decimal place. Exceptionally, P values less than 0.001 will be reported as “P < 0.001” or “< 0.001.”
- 2) Mean, standard deviation, geometric mean, adjusted mean, estimate of difference, and confidence interval  
Values will be rounded off to one digit after the last place of the significant digits of the data.
- 3) Minimum, median, maximum, and quartiles  
Values will be presented by the significant digits of the data.
- 4) Proportion, estimate and CI of incidence, and geometric coefficient of variation (CV)  
Values will be rounded off to the first decimal place.

### 5.2 Reporting of Prior ITP Medications, Concomitant Medications, and Rescue Medications

Prior ITP medications, concomitant medications, and rescue medications will be coded using the World Health Organization Drug Dictionary (WHO-DD) Global and reported with the following categories and Standardized Medication Names.

- Prior ITP medication categories: Corticosteroids, Rituximab, Thrombopoietin Receptor Agonists, Intravenous Immunoglobulins, Immunosuppressants, and Other
- Concomitant medication categories: ATC Level 3 Class Code
- Rescue medication categories: Platelet Transfusion, Intravenous Immunoglobulins, Intravenous Methylprednisolone, Oral Dexamethasone, Oral Prednisolone, and Other.

### 5.3 Reporting of Complications, Adverse Events, and Adverse Drug Reactions

Primary System Organ Classes (SOCs) and Preferred Terms (PTs) will be reported according to Medical Dictionary for Regulatory Activities (MedDRA).

For adverse events (AEs) of interest, event categories will be presented instead of primary SOCs. Subcategories will be set and reported for gastrointestinal complaints among AEs of interest. Category-based data summarization will also include subcategory-based summarization.

AEs for which more than one action was taken with the study drug will be reported with the highest level of action taken (discontinuation > dose reduction > interruption).

The definition of AEs of interest is shown in [Table 5.3-1](#).

Table 5.3-1 Adverse Events of Interest

AEs of interest (category)	Applicable PT (PT code)
Bleeding events	Conjunctival haemorrhage (10010719), Epistaxis (10015090), Haemorrhage subcutaneous (10018999), Menorrhagia (10027313), Mouth haemorrhage (10028024), Purpura (10037549), Contusion (10050584), Procedural haemorrhage (10071229)
Gastrointestinal complaints	AEs that fall under the following subcategories:
Nausea	Nausea (10028813)
Vomiting	Vomiting (10047700)
Non-infectious diarrhea SMQ	Diarrhoea (10012735)
Abdominal pain	Abdominal discomfort (10000059), Abdominal pain (10000081), Abdominal pain upper (10000087)
Infection	Cellulitis (10007882), Cystitis (10011781), Diarrhoea infectious (10012742), Diverticulitis (10013538), Gastroenteritis (10017888), Gingivitis (10018292), Herpes zoster (10019974), Nasopharyngitis (10028810), Otitis media (10033078), Paronychia (10034016), Periodontitis (10034539), Pulpitis dental (10037464), Urinary tract infection (10046571), Viral infection (10047461), Tinea infection (10060889), COVID-19 (10084268)
Hypertension SMQ	Blood pressure increased (10005750), Hypertension (10020772)
Neutropenia	Neutropenia (10029354), Neutrophil count decreased (10029366)
Drug related hepatic disorders SMQ	Alanine aminotransferase increased (10001551), Aspartate aminotransferase increased (10003481), Autoimmune hepatitis (10003827), Blood bilirubin increased (10005364), Hepatic cyst (10019646), Hepatic function abnormal (10019670), Hepatic steatosis (10019708), Liver function test abnormal (10024690), Hepatic enzyme increased (10060795), Liver function test increased (10077692)
Thrombosis, embolism, and thromboembolism	Not applicable

## 5.4 Handling of Drug Concentration Data

Measurements below the limit of quantification (LOQ) for the plasma R406 concentration will be handled as 0 (LOQ: 2.5 ng/mL). Plasma R406 concentration data collected during interruption of R788 will be excluded from the analysis. When calculating the geometric mean and geometric CV, if the measured value before logarithmic transformation is 0, it will be handled as missing.

## 5.5 Handling of Laboratory and Immunoglobulin Test Data

Values below the LOQ in laboratory and immunoglobulin tests will be handled as the LOQ.

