	allowed ITP therapies can be re-escalated based on the investigator's decision.
2) Platelet counts > 150000/μL and	Leave the dose of the allowed ITP therapy unchanged.
$\leq 250000/\mu L$	Monitor the platelet count until stable to assure it does not exceed
	250000/µL (the frequency of additional measurements will be
	determined by the investigator).

6) Rescue therapy

Rescue therapy may be used at the discretion of the investigator from the start of the study drug in Period I to the end of the follow-up period or market authorization for subjects who meet any one or both of the

Version: 1.0

following conditions.

- Platelet count $< 50000/\mu L$ and at immediate risk of bleeding or with clinically significant bleeding or wet purpura.
- Platelet count $< 50000/\mu L$ and requires urgent or emergent surgery. The drugs listed in Table 7 can be used for rescue therapy. The investigator should determine the dose and administration of rescue therapy with reference to Table 7.

Table 7 Rescue Therapy

Drug	Doses/regimens				
Platelet transfusion	10 to 20 units/dose				
Intravenous immunoglobulin	400 mg/kg/day for 5 consecutive days				
Intravenous methylprednisolone	1 g/day for 3 consecutive days				
Oral dexamethasone	Up to 40 mg/day for 1 to 2 days				
Oral prednisolone	Up to 1 mg/kg/day for 1 to 3 days				

7) Washout

Prior to start of the study drug administration in Period I, the use of all ITP medications except the allowed ITP therapies are prohibited during the specific period as shown in Table 8.

Table 8 Washout Period

Drug	Prohibited period prior to study drug administration
Cyclosporine or mycophenolate mofetil	2 weeks
Eltrombopag olamine	2 weeks
Romiplostim	3 weeks
Alkylating agents	8 weeks
Rituximab or other anti-CD20 monoclonal antibodies	24 weeks

Study assessments/procedures and time points:

See the study schedule table.

Number of subjects

Twenty-four subjects (16 in the Period I R788 group and 8 in the Period I placebo group)

Version: 1.0

Study Schedule Table for Period I

Study Schedule			iou i															F 11
	Informed consent	Screenin	ng period		Period I										Withdrawal	Follow-up period		
	_	Visit 1	Visit 2	Visit 3	Visit 4	Visit 5	Visit 6	Visit 7	Visit 8	Visit 9	Visit 10	Visit 11	Visit 12	Visit 13	Visit 14	Visit 15	_	The end of follow-up
	_	Screening A	Screening B	Day 1	Week 2	Week 4	Week 6	Week 8	Week 10	Week 12 a)	Week 14 a)	Week 16 a)	Week 18 a)	Week 20 a)	Week 22 a)	Week 24	_	2 weeks after Withdrawal Visit

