4.2.2 Rationale for safety endpoints

In addition to general safety endpoints, an immunoglobulin test was set, considering the action mechanism of R788. The ITP Bleeding Score was also set as a safety endpoint, considering the characteristics of the target disease.

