5.3 Withdrawal in Individual Subjects

5.3.1 Withdrawal criteria (withdrawal in individual subjects)

- 1) Adverse events
 - If the investigator judges that the adverse event requires withdrawal from the study.
 - If the subject does not wish to continue the study due to the adverse event.
- 2) Lack of efficacy (inadequate response)
 - If the investigator determines that there is an unacceptable risk for the subject to continue due to lack of efficacy of the study drug. The lack of efficacy of the study drug will be determined with reference to the following.

(1) Period I

- Subjects with a platelet count of $\geq 15000/\mu L$ on Day 1:
 - a) Platelet count of $< 50000/\mu$ L after Week 12 despite the increased dose to 150 mg *bid* for more than 4 weeks.
 - b) Platelet count of $< 50000/\mu$ L after Week 12 because of the inability to increase the dose to 150 mg *bid* due to possible poor tolerability.
- Subjects with platelet count of $< 15000/\mu$ L on Day 1:
 - a) Platelet count increase of $< 20000/\mu$ L from Day 1 after Week 12 despite the increased dose to 150 mg *bid* for more than 4 weeks.
 - b) Platelet count increase of $< 20000/\mu$ L from Day 1 after Week 12 because of the inability to increase the dose to 150 mg *bid* due to possible poor tolerability.
- Requirement for rescue therapy from Week 10 to platelet test at Week 24.
- (2) Periods II and III
 - Subjects who complete Period I:
 - a) Platelet count remains $< 50000/\mu$ L despite the increase dose to 150 mg *bid* for more than 4 weeks after the start of the study treatment in Period I.

b) Platelet count remains $< 50000/\mu$ L because of the inability to increase the dose to 150 mg *bid* due to possible poor tolerability.

- Subjects who meet all the "8.3.1 Transition criteria to Period II for subjects who withdraw from" (hereinafter referred to as early transition subjects):
 - a) Platelet count remains $< 50000/\mu$ L after ET Week 12 despite the treatment with 150 mg *bid* for at least 4 weeks after the start of the study treatment in Period II.
 - b) Platelet count remains at < 50000/µL after ET Week 12 because of the inability to increase the dose to 150 mg *bid* after the start of the study treatment in Period II due to possible poor tolerability.

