10.6 Immunoglobulin Test

Serum immunoglobulin levels (immunoglobulins M, G, and A) will be measured in the designated central laboratory. The presence or absence of sample collection will be recorded on the CRF.

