11.8 At Withdrawal

11.8.1 Withdrawal Visit

Subjects will undergo the Withdrawal Visit when they withdraw from Period I and do not transition to Period II, when they withdraw from Period III, or when they withdraw from Period III. Early transition subjects will not undergo the Withdrawal Visit. When the tests/examinations and evaluations on ET Day 1 do not meet "8.3.1 Transition criteria to Period II for subjects who withdraw from ," the tests/examinations and evaluations on ET Day 1 will be considered as those for Withdrawal Visit. Subjects who withdraw from the Non-dosing period will not undergo the Withdrawal Visit.

- QOL evaluation (SF-36)^{a)}
- Study drug compliance
- ITP Bleeding Score
- Adverse events/concomitant medications
- ECOG Performance Status
- 12-lead ECG^{b)}
- Vital signs
- Laboratory tests (hematology, serum chemistry, and urinalysis)
- Immunoglobulin test^{c)}
- Pregnancy test (women of childbearing potential only)
- Pharmacokinetics^{d)}
- a) The QOL evaluation should be performed only for subjects who withdraw from Period I and do not transition to Period II or subjects who withdraw from Period II. If the QOL evaluation is performed, it should be performed before the other tests/examinations and evaluations.
- b) The 12-lead ECG should be performed only for subjects who withdraw from Period I and do not transition to Period II or subjects who withdraw from Period II. In principle, the 12-lead ECG is taken before vital signs, laboratory tests, immunoglobulin test, immunological test, pregnancy test (women of childbearing potential only), and pharmacokinetics.
- c) The Immunoglobulin test should be performed only for subjects who withdraw from Period I and do not transition to Period II or subjects who withdraw from Period II.
- d) Pharmacokinetics should be examined only for subjects who withdraw from Period I and do not transition to Period II. The

time of the last study drug administration before blood sampling to the date of blood sampling are not specified.

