### 5.5.1 Handling of platelet count data

Any platelet count data obtained within 4 weeks (28 days) after the use of a rescue medication will be handled as missing in the efficacy evaluation.

In the analysis of the primary endpoint, missing data will be imputed except for data from subjects who discontinued due to an AE or lack of efficacy or those who used a rescue medication between Week 10 and Week 24. For details, see “[11.1.1 Analysis methods for the primary endpoint](#).”

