#### **12.4.4 Shift tables of laboratory and immunoglobulin tests**

For measurements obtained before and after administration, the number and percentages of subjects with low, normal, or high values will be presented.

Applicable analysis visit: Baseline, LOV

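### IgG measured after IVIG rescue can enter the descriptive immunoglobulin tables unflagged, where it may hide or mimic a drug-related change

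*SAP*

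**What the plan says.** Protocol 10.6 defines the assay: "Serum immunoglobulin levels (immunoglobulins M, G, and A) will be measured in the designated central laboratory". Protocol 4.2.2 gives the reason for it: "an immunoglobulin test was set, considering the action mechanism of R788". Protocol 1.3 describes that mechanism as including B-cell receptor signalling, with possible inhibition of antiplatelet antibody production.

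IVIG is one of five rescue options and may be used from the start of study drug onward (Protocol 8.7.8). The listed regimen is "400 mg/kg/day for 5 consecutive days" (Synopsis, Table 7).

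For immunoglobulin data, SAP 5.5 states one rule: "Values below the LOQ in laboratory and immunoglobulin tests will be handled as the LOQ". The next subsection, 5.5.1, has a post-rescue rule, but for another variable: "Any platelet count data obtained within 4 weeks (28 days) after the use of a rescue medication will be handled as missing". That sentence goes on to limit the rule to the efficacy evaluation.

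The affected outputs are:
- SAP 12.4.1: summary statistics of values and of changes from Day 1 of Period I (Period I, long-term treatment, Period II and non-dosing period).
- SAP 12.4.2: scatter plots of baseline against the last observed visit (LOV).
- SAP 12.4.4: baseline-to-LOV shift tables, in which "the number and percentages of subjects with low, normal, or high values will be presented".

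**The concern.** IVIG is infused immunoglobulin and the endpoint is serum immunoglobulin. I assume that the infused product is mainly IgG; the documents say only immunoglobulin. A result taken soon after rescue then measures the rescue as well as the study drug.

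Given the mechanism, the signal of interest is a fall in IgG. In an R788 subject, infused IgG can hide a fall. In a placebo subject, it can make R788 look lower by comparison. An affected R788 subject can also appear to show a rise. With 16 and 8 subjects planned, and Week 24 plus LOV as the only on-treatment immunoglobulin time points in Period I (SAP Table 5.9-1), one such value carries visible weight and nothing in the table tells the reader that it is there.

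**Working it through.** **Step 1. Is there any rule that removes or flags these values?**
- SAP 5.5: LOQ substitution only.
- SAP 5.5.1: rescue rule for platelet counts, efficacy evaluation only.
- SAP 5.9: drops out-of-window and unscheduled results from time-point summaries, and tests later than the last dose plus 3 days (Period I) or 7 days (Periods II and III). None of these depends on rescue.
- SAP 6.2: data are left as they are apart from the exceptions listed there and in section 5; none concerns immunoglobulins after rescue.
- SAP 12.4 and Protocol 14.6.5: no rescue exclusion, flag or supportive table.
- SAP 5.2 and 10.7: rescue use is tabulated by type, but is not linked to the immunoglobulin results.

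So no rule exists in the documents. The table shells are separate (SAP 15) and are not available here.

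**Step 2. Where can a post-IVIG test qualify?**
- *Week 24*, if a rescued subject stays in Period I.
- *Withdrawal Visit as LOV.* Protocol 5.3.1 lists, as a reference for judging lack of efficacy in Period I, "Requirement for rescue therapy from Week 10 to platelet test at Week 24". Protocol 11.8.1, footnote c, places the test at that visit: "The Immunoglobulin test should be performed only for subjects who withdraw from Period I and do not transition to Period II"; it goes on to include withdrawals from Period II. The visit counts as LOV only within the 3- or 7-day limit.
- *Period II:* Week 52 (or ET Week 28) and LOV.
- *Non-dosing period.* Subjects given rescue move to Period III (Protocol 8.5), and Period III Day 1 includes the test (Protocol 11.7.1). SAP 5.9 treats that day as Week 4 of the non-dosing period, and its non-dosing LOV takes the latest test up to the end of the period. This route reaches 12.4.1 only.

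Baseline is largely protected: exclusion criteria 16 and 17 bar blood products and IVIG before Day 1. Within a subject, the distortion therefore falls on the post-baseline value.

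**Step 3. Illustrative size.** The plan gives no figure on this point, so there is none to reproduce.
- Listed course: 400 mg/kg × 5 = 2000 mg/kg = 2.0 g/kg.
- Rise at end of course = dose × intravascular share ÷ plasma volume. Assumed share 0.4 to 1.0 and plasma volume 0.04 to 0.05 L/kg: from 2.0 × 0.4 ÷ 0.05 = 16 g/L to 2.0 × 1.0 ÷ 0.04 = 50 g/L.
- Residual after *d* days = rise × 0.5^(*d* ÷ half-life). Assumed half-life 14 to 35 days. At 28 days: from 16 × 0.5^2 = 4 g/L to 50 × 0.5^0.8 = 29 g/L. At 18 weeks (126 days; for example, rescue at Week 6 and test at Week 24): from 16 × 0.5^9 = 0.03 g/L to 50 × 0.5^3.6 = 4 g/L.
- An assumed residual of 500 to 2000 mg/dL (5 to 20 g/L) lies inside the 28-day range.
- Shift in group mean from one affected subject = residual ÷ n, with planned sizes from Protocol 8.9.1:
  - placebo, n=8: 500 ÷ 8 = 63 to 2000 ÷ 8 = 250 mg/dL
  - R788, n=16: 500 ÷ 16 = 31 to 2000 ÷ 16 = 125 mg/dL
- In the shift table, one subject is 1 ÷ 8 = 12.5% of placebo and 1 ÷ 16 = 6.25% of R788.

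If fewer subjects have a value at the visit, the shift is larger in proportion.

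**The case against.** The strongest reply is that the plan is consistent. It applies a rescue rule to efficacy platelets and reports safety laboratory data as observed; platelets listed as a safety variable in SAP 12.4 get no rescue rule either. The immunoglobulin outputs have no test and no between-group difference, and SAP 6.5.2 treats non-primary variables as reference only. Medians and quartiles are also given, which one outlying value moves little. In a trial of 24, the scatter plots, the listing of abnormal laboratory values (SAP 12.6) and the rescue tables help a reader trace an outlier.

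Much of this stands and limits the importance of the point. It does not close the gap. Platelets have a separate efficacy analysis in which the rescue rule applies; IgG has no such second output. A listing of abnormal values also misses the case that matters most: a fall that infused IgG has brought back into the normal range.

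Four stronger readings are tempting, and the documents do not support them.
- *Every post-IVIG value enters.* SAP 5.9 removes some by window, unscheduled status or days since last dose.
- *Rescue leads automatically to a distorted LOV.* Withdrawal is the investigator's judgement, rescue need not be IVIG, the listed IVIG dose is a reference, and the Withdrawal Visit must fall within the last-dose limit.
- *IVIG before ET Day 1 distorts the Period II changes.* IVIG rescue is allowed in the 2 weeks before ET Day 1 (Protocol 8.3.1), but SAP 5.9 evaluates changes only after Day 1 of each period. The ET Day 1 value can enter the summary of measured values, and both Period II groups receive open-label R788. Early transition subjects have no Withdrawal Visit.
- *Placebo IgG is inflated, giving a false fall on R788.* No rescue rate by arm is given for this trial. Protocol 4.1.2 says only that overall response went with less rescue use overseas.

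**Conclusion.** The omission is real: a qualifying IgG result taken after IVIG enters 12.4.1, and where it is the LOV in Period I, long-term treatment or Period II also 12.4.2 and 12.4.4, with nothing to mark it. It can hide or mimic a drug-related change in a marker chosen for the drug's mechanism. Whether it does depends on how often IVIG is given near a test, which the documents do not say. Early Period I rescue would have largely cleared by Week 24 over most of the assumed half-life range.

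The illustrative mean shifts are per affected subject. They rest on an assumed residual of 500 to 2000 mg/dL, on IVIG being mainly IgG, and on the planned group sizes. Net direction between arms cannot be stated. The consequence is confined to the interpretation of descriptive safety tables. The change is worth making because it costs little.

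**What to change.** In SAP 5.5, add a rule that flags every immunoglobulin value obtained after the first dose of IVIG given as rescue, using the rescue drug and dates already recorded on the CRF (Protocol 10.3.2). Present 12.4.1, 12.4.2 and 12.4.4 twice: as observed, and with flagged values set to missing. List the flagged values by subject with the IVIG dates.

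Two shortcuts should be avoided:
- Do not replace a flagged LOV with the last value before IVIG. In Period I that would usually be Day 1 and would force a change of zero.
- Do not borrow the 28-day platelet window unless it is justified for IgG. Under the assumptions above, 4 to 29 g/L could remain at 28 days.

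The cost is one sentence in the SAP, one filter, and one extra set of descriptive outputs, with a few fewer IgG values in the restricted version.
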